10.5.2.3 Other safety data

Electrocardiogram

ECG will be performed at Baseline and after 12 months. Abnormalities will be reported together with an overall interpretation of the findings. Any abnormalities at Baseline will be summarized. The investigator will flag all abnormalities which are new or worsened since Baseline. All new or worsened abnormalities will be recorded on the AE eCRF page. All findings of patients with new or worsened clinically significant abnormalities will be listed.

Vital signs

Vital signs and body weight measured more than 30 days after discontinuation of study medication will be excluded from the analysis.

The absolute change from Baseline weight will be summarized by scheduled visit with n, mean, SD, minimum, median, and maximum values.

The criteria for notably abnormal vital signs and weight are displayed in Table 10-2.

Table 10-2 Definition of notable ranges for vital signs and weight

Parameter	Criteria for notable ranges
Systolic blood pressure	≥ 180 mmHg/≤ 90 mmHg with increase/decrease from Baseline of ≥ 20 mmHg
Diastolic blood pressure	≥ 105 mmHg/≤ 50 mmHg with increase/decrease from Baseline of ≥ 15 mmHg
Pulse rate	≥ 120 bpm/≤ 50 bpm with increase/decrease from Baseline of ≥ 15 bpm
Weight	≥ 7% increase or decrease from Baseline weight

10.5.2.4 Supportive analyses for secondary objectives

Not applicable.

10.5.2.5 Tolerability

Not applicable.

10.5.3 Resource utilization

Not applicable.

10.5.4 Patient-reported outcomes

Not applicable.

10.6 Exploratory objectives

Not applicable.

10.7 Interim analysis

Not applicable.

10.8 Sample size calculation

No formal sample size has been calculated. All patients enrolled into the CICL670F2201 study who have completed 24 months treatment will be offered participation in this current protocol and those consenting to participate will contribute to the pool of data.

According to enrolment of CICL670F2201 in Region Europe, a maximum of 90 patients should be eligible for enrollment in this study.

10.9 Power for analysis of key secondary variables

Not applicable.

11 Ethical considerations and administrative procedures

11.1 Regulatory and ethical compliance

This clinical study was designed, shall be implemented and reported in accordance with the ICH Harmonized Tripartite Guidelines for Good Clinical Practice, with applicable local regulations (including European Directive 2001/20/EC and US Code of Federal Regulations Title 21), and with the ethical principles laid down in the Declaration of Helsinki.

11.2 Responsibilities of the investigator and IRB/IEC/REB

The protocol and the proposed informed consent form must be reviewed and approved by a properly constituted Institutional Review Board/Independent Ethics Committee/Research Ethics Board (IRB/IEC/REB) before study start. Prior to study start, the investigator is required to sign a protocol signature page confirming his/her agreement to conduct the study

in accordance with these documents and all of the instructions and procedures found in this protocol and to give access to all relevant data and records to Novartis monitors, auditors, Novartis Clinical Quality Assurance representatives, designated agents of Novartis, IRBs/IECs/REBs and regulatory authorities as required.

11.3 Informed consent procedures

Eligible patients may only be included in the study after providing written (witnessed, where required by law or regulation), IRB/IEC/REB-approved informed consent or, if incapable of doing so, after such consent has been provided by a legally acceptable representative of the patient. In cases where the patient's representative gives consent, the patient should be informed about the study to the extent possible given his/her understanding. If the patient is capable of doing so, he/she should indicate assent by personally signing and dating the written informed consent document or a separate assent form.

Informed consent must be obtained before conducting any study-specific procedures (i.e. all of the procedures described in the protocol). The process of obtaining informed consent should be documented in the patient source documents. The date when a subject's Informed Consent was actually obtained will be captured in their CRFs.

Novartis will provide to investigators, in a separate document, a proposed informed consent form (ICF) that is considered appropriate for this study and complies with the ICH GCP guideline and regulatory requirements. Any changes to this ICF suggested by the investigator must be agreed to by Novartis before submission to the IRB/IEC/REB, and a copy of the approved version must be provided to the Novartis monitor after IRB/IEC/REB approval.

Women of child bearing potential should be informed that taking the study medication may involve unknown risks to the fetus if pregnancy were to occur during the study and agree that in order to participate in the study they must adhere to the contraception requirement for the duration of the study. If there is any question that the patient will not reliably comply, they should not be entered in the study.

Additional consent form

Not applicable.

11.4 Discontinuation of the study

Novartis reserves the right to discontinue this study under the conditions specified in the clinical study agreement. Specific conditions for terminating the study are outlined in Section 4.4.

11.5 Publication of study protocol and results

Novartis is committed to following high ethical standards for reporting study results for its innovative medicine, including the timely communication and publication of clinical trial results, whatever their outcome. Novartis assures that the key design elements of this protocol will be posted on the publicly accessible database e.g. www.clinicaltrials.gov before study start. In addition, results of interventional clinical trials in adult patients are posted on www.novartisclinicaltrials.com, a publicly accessible database of clinical study results within

1 year of study completion (i.e., LPLV), those for interventional clinical trials involving pediatric patients within 6 months of study completion.

Novartis follows the ICMJE authorship guidelines (www.icmje.org) and other specific guidelines of the journal or congress to which the publication will be submitted.

Authors will not receive remuneration for their writing of a publication, either directly from Novartis or through the professional medical writing agency. Author(s) may be requested to present poster or oral presentation at scientific congress; however, there will be no honorarium provided for such presentations.

As part of its commitment to full transparency in publications, Novartis supports the full disclosure of all funding sources for the study and publications, as well as any actual and potential conflicts of interest of financial and non-financial nature by all authors, including medical writing/editorial support, if applicable.

For the Novartis Guidelines for the Publication of Results from Novartis-sponsored Research, please refer to www.novartis.com.

11.6 Study documentation, record keeping and retention of documents

Each participating site will maintain appropriate medical and research records for this trial, in compliance with Section 4.9 of the ICH E6 GCP, and regulatory and institutional requirements for the protection of confidentiality of subjects. As part of participating in a Novartis-sponsored study, each site will permit authorized representatives of the sponsor(s) and regulatory agencies to examine (and when required by applicable law, to copy) clinical records for the purposes of quality assurance reviews, audits and evaluation of the study safety and progress.

Source data are all information, original records of clinical findings, observations, or other activities in a clinical trial necessary for the reconstruction and evaluation of the trial. Examples of these original documents and data records include, but are not limited to, hospital records, clinical and office charts, laboratory notes, memoranda, subjects' diaries or evaluation checklists, pharmacy dispensing records, recorded data from automated instruments, copies or transcriptions certified after verification as being accurate and complete, microfiches, photographic negatives, microfilm or magnetic media, x-rays, and subject files and records kept at the pharmacy, at the laboratories, and medico-technical departments involved in the clinical trial

Data collection is the responsibility of the clinical trial staff at the site under the supervision of the site Principal Investigator. The study case report form (eCRF) is the primary data collection instrument for the study. The investigator should ensure the accuracy, completeness, legibility, and timeliness of the data reported in the eCRFs and all other required reports. Data reported on the eCRF, that are derived from source documents, should be consistent with the source documents or the discrepancies should be explained. All data requested on the eCRF must be recorded. Any missing data must be explained. For electronic CRFs an audit trail will be maintained by the system.

The investigator/institution should maintain the trial documents as specified in Essential Documents for the Conduct of a Clinical Trial (ICH E6 Section 8) and as required by applicable regulations and/or guidelines. The investigator/institution should take measures to prevent accidental or premature destruction of these documents.

Essential documents (written and electronic) should be retained for a period of not less than fifteen (15) years from the completion of the Clinical Trial unless Sponsor provides written permission to dispose of them or, requires their retention for an additional period of time because of applicable laws, regulations and/or guidelines.

11.7 Confidentiality of study documents and patient records

The investigator must ensure anonymity of the patients; patients must not be identified by names in any documents submitted to Novartis. Signed informed consent forms and patient enrollment log must be kept strictly confidential to enable patient identification at the site.

11.8 Audits and inspections

Source data/documents must be available to inspections by Novartis or designee or Health Authorities.

11.9 Financial disclosures

Financial disclosures should be provided by study personnel who are directly involved in the treatment or evaluation of patients at the site - prior to study start.

12 Protocol adherence

Investigators ascertain they will apply due diligence to avoid protocol deviations. Under no circumstances should the investigator contact Novartis or its agents, if any, monitoring the study to request approval of a protocol deviation, as no authorized deviations are permitted. If the investigator feels a protocol deviation would improve the conduct of the study this must be considered a protocol amendment, and unless such an amendment is agreed upon by Novartis and approved by the IRB/IEC/REB it cannot be implemented. All significant protocol deviations will be recorded and reported in the CSR.

14.1 Dosing tables (Deferasirox FCT)

To guide the investigator and/or pharmacist on the number of deferasirox FCT tablets of a given strength to prescribe to a given patient, taking into account the patient's body weight and protocol specified dosing scheme described above, a table is provided below. Where the calculated dose cannot be constituted by the available tablet strengths, the closest dose is applied. An example illustrating this approach is provided here below:

For a patient whose body weight is 46 kg, and whose planned deferasirox FCT dose is 14 mg/kg/day, the calculated deferasirox FCT daily dose would be 644 mg. So taking into account the available strengths of 90, 180 and 360 mg deferasirox FCT tablets, the patient should receive the closest daily dose of 630 mg which can be easily constituted by taking $1 \times 90 \text{ mg} + 1 \times 180 \text{ mg} + 1 \times 360 \text{ mg}$ deferasirox FCT tablets = 3 tablets.

The dosing tables below have been constructed with cut-offs for lower and upper body weights being 20 and 147 kg respectively depending on the dose administered. This is taking into account that CICL670F2201 study enrolled male or female patients \geq 10 years.

Table 14-1 Deferasirox FCT dosing table for 3.5 mg/kg/day

Pt Weight in kg	Closest Dose (mg)	90 mg	180 mg	360 mg
20 - 38	90	1		
39 - 64	180		1	
65 - 89	270	1	1	
90 - 115	360			1
116 - 141	450	1		1

Table 14-2 Deferasirox FCT dosing table for 7 mg/kg/day

Pt Weight in kg	Closest Dose (mg)	90 mg	180 mg	360 mg
20 - 32	180		1	
33 - 44	270	1	1	
45 - 57	360			1
58 - 70	450	1		1
71 - 83	540		1	1
84 - 96	630	1	1	1
97 - 109	720			2
110 - 122	810	1		2
123 - 134	900		1	2
135 - 147	990	1	1	2

Table 14-3 Deferasirox FCT dosing table for 10.5 mg/kg/day

Pt Weight in kg	Closest Dose (mg)	90 mg	180 mg	360 mg
20 - 21	180		1	
22 - 29	270	1	1	
30 - 38	360			1
39 - 46	450	1		1
47 - 55	540		1	1
56 - 64	630	1	1	1
65 - 72	720			2
73 - 81	810	1		2
82 - 89	900		1	2
90 - 98	990	1	1	2
99 - 106	1080			3
107 - 115	1170	1		3
116 - 124	1260		1	3
125 - 132	1350	1	1	3
133 - 141	1440			4

Table 14-4 Deferasirox FCT dosing table for 14 mg/kg/day

		-		
Pt Weight in kg	Closest Dose (mg)	90 mg	180 mg	360 mg
20 - 22	270	1	1	
23 - 28	360			1
29 - 35	450	1		1
36 - 41	540		1	1
42 - 47	630	1	1	1
48 - 54	720			2
55 - 60	810	1		2
61 - 67	900		1	2
68 - 73	990	1	1	2
74 - 80	1080			3
81 - 86	1170	1		3
87 - 92	1260		1	3
93 - 99	1350	1	1	3
100 - 105	1440			4
106 - 112	1530	1		4
113 - 118	1620		1	4
119 - 125	1710	1	1	4
126 - 131	1800			5
132 - 137	1890	1		5
138 - 144	1980		1	5

Table 14-5 Deferasirox FCT dosing table for 17.5 mg/kg/day

Pt Weight in kg	Closest Dose (mg)	90 mg	180 mg	360 mg
20 - 23	360			1
24 - 28	450	1		1
29 - 33	540		1	1
34 - 38	630	1	1	1
39 - 43	720			2
44 - 48	810	1		2
49 - 53	900		1	2
54 - 59	990	1	1	2
60 - 64	1080			3
65 - 69	1170	1		3
70 - 74	1260		1	3
75 - 79	1350	1	1	3
80 - 84	1440			4
85 - 89	1530	1		4
90 - 95	1620		1	4
96 - 100	1710	1	1	4
101 - 105	1800			5
106 - 110	1890	1		5
111 - 115	1980		1	5
116 - 120	2070	1	1	5
121 - 125	2160			6
126 - 131	2250	1		6
132 - 136	2340		1	6
137 - 141	2430	1	1	6

Table 14-6 Deferasirox FCT dosing table for 21 mg/kg/day

Pt Weight in kg	Closest Dose (mg)	90 mg	180 mg	360 mg
20 - 23	450	1		1
24 - 27	540		1	1
28 - 31	630	1	1	1
32 - 36	720			2
37 - 40	810	1		2
41 - 44	900		1	2
45 - 48	990	1	1	2
49 - 53	1080			3
54 - 57	1170	1		3
58 - 61	1260		1	3
62 - 66	1350	1	1	3

Pt Weight in kg	Closest Dose (mg)	90 mg	180 mg	360 mg
67 - 70	1440			4
71 - 74	1530	1		4
75 - 78	1620		1	4
79 - 83	1710	1	1	4
84 - 87	1800			5
88 - 91	1890	1		5
92 - 96	1980		1	5
97 - 100	2070	1	1	5
101 - 104	2160			6
105 - 108	2250	1		6
109 - 113	2340		1	6
114 - 117	2430	1	1	6
118 - 121	2520			7
122 - 126	2610	1		7
127 - 130	2700		1	7
131 - 134	2790	1	1	7
135 - 138	2880			8
139 - 143	2970	1		8

Table 14-7 Deferasirox FCT dosing table for 24.5 mg/kg/day

Pt Weight in kg	Closest Dose (mg)	90 mg	180 mg	360 mg
20 - 23	540		1	1
24 - 27	630	1	1	1
28 - 30	720			2
31 - 34	810	1		2
35 - 38	900		1	2
39 - 41	990	1	1	2
42 - 45	1080			3
46 - 49	1170	1		3
50 - 52	1260		1	3
53 - 56	1350	1	1	3
57 - 60	1440			4
61 - 63	1530	1		4
65 - 67	1620		1	4
68 - 71	1710	1	1	4
72 - 74	1800			5
75 - 78	1890	1		5
79 - 82	1980		1	5
83 - 85	2070	1	1	5

Pt Weight in kg	Closest Dose (mg)	90 mg	180 mg	360 mg
86 - 89	2160			6
90 - 93	2250	1		6
94 - 97	2340		1	6
98 - 100	2430	1	1	6
101 - 104	2520			7
105 - 108	2610	1		7
109 - 111	2700		1	7
112 - 115	2790	1	1	7
116 - 119	2880			8
120 - 122	2970	1		8
123 - 126	3060		1	8
127 - 130	3150	1	1	8
131 - 133	3240			9
134 - 137	3330	1		9
138 - 141	3420		1	9

Table 14-8 Deferasirox FCT dosing table for 28 mg/kg/day

Pt Weight in kg	Closest Dose (mg)	90 mg	180 mg	360 mg
21 - 24	630	1	1	1
25 - 27	720			2
28 - 30	810	1		2
31 - 33	900		1	2
34 - 36	990	1	1	2
37 - 40	1080			3
41 - 43	1170	1		3
44 - 46	1260		1	3
47 - 49	1350	1	1	3
50 - 52	1440			4
53 - 56	1530	1		4
57 - 59	1620		1	4
60 - 62	1710	1	1	4
63 - 65	1800			5
66 - 69	1890	1		5
70 - 72	1980		1	5
73 - 75	2070	1	1	5
76 - 78	2160			6
79 - 81	2250	1		6
82 - 85	2340		1	6

Pt Weight in kg	Closest Dose (mg)	90 mg	180 mg	360 mg
86 - 88	2430	1	1	6
89 - 91	2520			7
92 - 94	2610	1		7
95 - 97	2700		1	7
98 - 101	2790	1	1	7
102 - 104	2880			8
105 - 107	2970	1		8
108 - 110	3060		1	8
111 - 114	3150	1	1	8
115 - 117	3240			9
118 - 120	3330	1		9
121 - 123	3420		1	9
124 - 126	3510	1	1	9
127 - 130	3600			10
131 - 133	3690	1		10
134 - 136	3780		1	10
137 - 139	3870	1	1	10
140 - 142	3960			11

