6.1.1 Dosing regimen

Having completed the 24 weeks of CICL670F2201, patients recruited at Region Europe participating sites will be invited to participate in this study to continue FCT or switch from DT to the FCT formulation. Patients completing CICL670F2201 and switching to commercially available DT or other ICT will still be eligible to enroll in this study after a 5-day washout period during the Screening period.

All patients randomized in the DT arm in CICL670F2201 and well-managed on treatment with deferasirox DT will use an equivalent FCT dose. Patient switching from DT will use an equivalent FCT dose at the start of this study corresponding to their DT dose at the end of CICL670F2201 (see Appendix 14.2). A patient who is receiving an adjusted dose at the time of completing CICL670F2201 will commence this study receiving that adjusted dose until a time when the investigator deems it necessary to adjust the dose. Patients who completed CICL670F2201 and had switched to commercially available DT or other ICT will have to undergo a 5-day washout period and will then be assigned FCT at a starting dose equivalent to their last deferasirox dose on CICL670F2201.

Dose adjustment for better treatment effects will be allowed every 3 months based on serum ferritin levels and the investigator's judgment. The dose adjustments will be performed in steps of 3.5 to 7 mg/kg/day for deferasirox FCT.

For each patient the daily dose is calculated by the physician based on the patient's actual body weight, and then rounded up or down to the nearest whole tablet according to the available strengths of deferasirox FCT tablets (90 mg, 180 mg and 360 mg, see Appendix 14.1). All doses planned and prescribed to the patient and all dose changes including reasons for change during the study must be recorded in the eCRF.

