6.3.1.1 Change in patient weight

The dose of study medication will be adapted using dosing table (provided in Appendix 14.1) during the study, if the change (increase or decrease) in body weight exceeds 10% of the body weight compared to the Visit 3 or the last dose adjustment due to change in patient body weight.

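### The dosing tables in Protocol Appendix 14.1 list a dose 90 mg above the closest one at 27 of 986 whole-kg weights, and Table 14-7 has no row for 64 kg

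*Protocol*

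**What the plan says.** Section 6.1.1 has the physician calculate the daily dose from actual body weight, which is then "rounded up or down to the nearest whole tablet according to the available strengths of deferasirox FCT tablets". Appendix 14.1 repeats the rule: "Where the calculated dose cannot be constituted by the available tablet strengths, the closest dose is applied". Its worked example is a 46 kg patient at 14 mg/kg/day, where "the calculated deferasirox FCT daily dose would be 644 mg" and "the patient should receive the closest daily dose of 630 mg". The dose column of each table is labelled as the closest dose in mg.

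Section 6.3.1.1 covers a body-weight change of more than 10%: "The dose of study medication will be adapted using dosing table (provided in Appendix 14.1) during the study". So the tables are a route to the dose that the protocol prescribes, as well as an illustration of the rule.

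In Table 14-7 the 1530 mg row covers 61 to 63 kg and the next row, 1620 mg, starts at 65 kg.

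**The concern.** If the tables depart from the rule, the protocol gives two answers for the same patient. A physician calculating under Section 6.1.1 and a pharmacist reading Appendix 14.1 would reach different mg doses, and each could cite the protocol. SAP Section 2.2 includes receipt of an incorrect dose among its protocol deviation categories, so each weight should have one correct dose.

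The affected levels are ones this population uses. The parent study's inclusion criteria (Protocol Section 5.2) required dispersible-tablet doses of at least 30 mg/kg/day in thalassemia and at least 20 mg/kg/day in MDS. Table 14-9 converts these to 21 and 14 mg/kg/day of the film-coated tablet. At 64 kg on 24.5 mg/kg/day, a site using the table finds no dose and must go back to the calculation.

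**Working it through.** **Inputs (Protocol Sections 6.1.1 and 14.1).** Tablets of 90, 180 and 360 mg, so the doses that can be made up are the multiples of 90 mg. The rule is the closest dose. The table levels are 3.5 to 28 mg/kg/day in steps of 3.5.

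**Formula.** Calculated dose = level × weight. Closest dose = the multiple of 90 mg with the smallest absolute distance from it. The implied cut-off is a remainder of 45 mg. Exact ties were accepted as correct.

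**Worked example reproduced.** 46 × 14 = 644 mg; 644 − 630 = 14 mg and 720 − 644 = 76 mg, so 630 mg, as the protocol says.

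**Every whole-kg entry checked.** The 174 rows hold 986 entries. Thirteen are exact ties, all rounded up. Twenty-seven list a dose that is not the closest, and all 27 are exactly 90 mg too high.

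| Table | mg/kg/day | Entries | Weights (kg) with listed dose 90 mg above closest | Largest remainder rounded down / smallest rounded up (mg) |
|---|---|---|---|---|
| 14-1 | 3.5 | 122 | none | 44 / 45 |
| 14-2 | 7 | 128 | none | 44 / 45 |
| 14-3 | 10.5 | 122 | 47, 107 | 42 / 43.5 |
| 14-4 | 14 | 125 | 48, 61, 93, 106, 138 | 40 / 42 |
| 14-5 | 17.5 | 122 | none | 42.5 / 45 |
| 14-6 | 21 | 124 | 32, 49, 62, 79, 92, 109, 122, 139 | 36 / 39 |
| 14-7 | 24.5 | 121 | 20, 31, 42, 53, 75, 86, 101, 112, 123, 134 | 36.5 / 37 |
| 14-8 | 28 | 122 | 53, 98 | 42 / 44 |

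Counts: 2 + 5 + 8 + 10 + 2 = 27, and 27/986 = 2.7%. Tables 14-4, 14-6, 14-7 and 14-8 hold 25 of them.

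**Examples.**
- 48 kg at 14: 672 mg calculated. Listed 720 is 48 mg away; 630 is 42 mg away.
- 86 kg at 24.5: 2107 mg calculated. Listed 2160 is 53 mg away; 2070 is 37 mg away (the largest gain, 53 − 37 = 16 mg).
- 101 kg at 24.5: 2474.5 mg calculated. Listed 2520 is 45.5 mg away; 2430 is 44.5 mg away (the smallest gain, 1 mg).
- 20 kg at 24.5: 490 mg calculated. Listed 540 is 50 mg away; 450 is 40 mg away (the largest relative excess, 50/490 = 10.2%).

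**Size over the 27.** The listed dose is 45.5 to 53 mg above the calculated dose (1.4% to 10.2%, median 3.1%). The closest dose is 37 to 44.5 mg below it (1.3% to 8.8%). The median gain from correction is 6 mg. The listed dose needs more tablets at 14 of the entries, the same number at 7 and fewer at 6. At 48 kg, for example, 720 mg is two tablets and 630 mg is three.

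**Consistency across tables.** Eight calculated doses are rounded down in one table and up in another: 490, 493.5, 672, 854, 1029, 1302, 1837.5 and 1932 mg. For example, 672 mg becomes 630 mg at 96 kg in Table 14-2 but 720 mg at 48 kg in Table 14-4.

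**64 kg at 24.5.** 64 × 24.5 = 1568 mg; 1568 − 1530 = 38 mg and 1620 − 1568 = 52 mg, so the closest dose is 1530 mg. This is the only gap between rows in the eight tables.

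**The case against.** The strongest reply is that the tables follow a scheme of their own. Convert each dose to a nominal whole-kg weight (dose divided by level), and start each row at the midpoint between neighbouring nominal weights, with halves rounded up. At 14 mg/kg/day, 630 mg gives 45 kg and 720 mg gives 51 kg; the midpoint is 48 kg, the listed start. This reproduces 164 of the 166 internal row starts and accounts for all 27 mismatches, so they stem from one approximation and not from 27 separate slips. Under that scheme the 1620 mg row of Table 14-7 would start at 64 kg, so the printed 65 may be a one-digit slip, or a misread of the PDF.

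As an explanation of origin, that stands. It does not reconcile the tables with the rule. Neither document states the scheme or gives the tables precedence over the closest-dose rule. A row of 64-67 kg at 1620 mg would close the gap but break the rule, because 1530 mg is closer at 64 kg.

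The points about size also stand. The true crossovers lie only 0.02 to 0.33 kg above the listed weights, and body weight is taken in indoor clothing (Section 7.2.2.3). Correct nearest-tablet rounding elsewhere in the tables deviates by up to 32% (38 kg at 3.5 mg/kg/day: 133 mg calculated, 90 mg given). The 2.7% is a share of table entries and not of patients; the documents give no weight or dose distribution. Section 6.1.1 still yields a dose at 64 kg. SAP Sections 2.2.1 and 2.5.1 use the recorded mg dose divided by current weight, so the exposure summaries do not depend on the tables.

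**Conclusion.** The concern holds, as a minor one. At 27 of 986 whole-kg entries the tables list a dose 90 mg above the one the protocol's rule requires, and 64 kg is missing from Table 14-7. The departures are always upward, but exceeding the nominal mg/kg dose is not itself the error, since correct rounding can do that too. The conclusion rests on three things: the closest-dose wording is read on the mg scale, as the worked example does; weights are taken in whole kg, as the rows are; and the printed row boundaries were extracted correctly. If the 65 is a misread 64, the gap disappears and a 28th mismatch takes its place.

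**What to change.** Lower the 27 entries by 90 mg. Move 26 row starts up by 1 kg in Tables 14-3, 14-4, 14-6, 14-7 and 14-8, with the preceding rows extended to match, and split the first row of Table 14-7 into 20 kg at 450 mg and 21-23 kg at 540 mg. Change the 1530 mg row of Table 14-7 to 61-64 kg. All 987 entries (986 + 1) then meet the rule, and no calculated dose is rounded two ways.

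If the sponsor would rather keep the tables, state in Sections 6.1.1 and 14.1 that the tabulated dose takes precedence over the closest-dose rule, and still add 64 kg.

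Either change is nearly free in an amendment or a corrected dosing aid; the boundary edits need a transcription check. The SAP amendment is dated August 2019, before database lock, so dosing may already have ended. In that case a one-line note in the clinical study report is enough.
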